2.13 Interim analysis

No formal interim analysis is planned for this study.

3 Sample size calculation

3.1.1 Primary endpoint

Based on medical experts' advice, it is postulated that approximately 15% of patients who do not respond or relapse after a first round of steroid therapy would have sustained response off treatment by 12 months if on steroid recycling. In this study, at least a 10% higher sustained response off treatment rate is expected by month 12, i.e., a sustained response off treatment rate of at least 25% by 12 months is expected in patients who will receive eltrombopag after failing first-line steroids.

The sample size calculation is based on an exact binomial test for single proportion using a target alpha level of 0.05 and power of 80% to compare the null hypothesis $H_0: P=0.15$ against the alternative hypothesis $H_1: P>0.15$, where P is proportion of patients with sustained response off treatment by Month 12.

A **sample size of 101** gives at least 80% power if the true sustained response off treatment rate with eltrombopag is 25% or more with an actual significance level of 0.043. The null hypothesis will be rejected if the number of patients with sustained response off treatment is 22 or more. [Table 3-1](#) shows the sample size, cut-off, actual alpha, beta and power for different sustained response off treatment rates. PASS 11 (version 11.0.10) is used for the sample size calculation.

Table 3-1 **Numeric results for testing $H_0: P = P_0$ versus $H_1: P > P_0$ using exact binomial test statistic**

Proportion given H_0 (P_0)	Proportion given H_1 (P_1)	Sample size (N)	Cut-off (Reject H_0 if $R \geq$ This)	Actual Alpha	Actual Beta	Actual Power
0.150	0.250	101	22	0.043	0.196	0.804
0.150	0.300	48	12	0.048	0.181	0.819
0.150	0.350	28	8	0.049	0.182	0.818
0.150	0.400	22	7	0.037	0.158	0.842
0.200	0.300	116	31	0.049	0.193	0.807
0.200	0.350	56	17	0.043	0.194	0.806
0.200	0.400	35	12	0.034	0.195	0.805

At the end of the study, for decision-making purposes, the cut-off will be determined based on the final sample size and the target alpha and beta.

3.1.2 Responders cut-off update due to final sample size

For decision-making purposes, responders cut-off will be determined based on the final sample size and the target alpha and beta.

A final sample size of 105 gives at least 80% power if the true sustained response rate on eltrombopag is 25% or more with an actual significance level of **0.037**. The null hypothesis will be rejected if the number of responders is **23** or more (instead of 22 for an initial sample size of 101 patients as stated in Protocol, section 12.8.1).

[Table 3-2](#) shows the sample size, cut-off, actual alpha, beta and power for different sample sizes.

Table 3-2 **Numeric results for testing $H_0: P = P_0$ versus $H_1: P > P_0$ using exact binomial test statistic, for a sample size of 101 and 105 patients**

Sample size (N)	Proportion given H_0 (P_0)	Proportion given H_1 (P_1)	Cut-off (Reject H_0 if $R \geq$ This)	Actual Alpha	Actual Beta	Actual Power
101	0.150	0.250	22	0.043	0.196	0.804
105	0.150	0.250	23	0.037	0.200	0.800

4 Changes to protocol specified analyses

In Section 6.2.3 of the study protocol there is stated that a patient who receives rescue medication or therapy will not be considered in having achieved sustained response off treatment for the primary endpoint, unless the patient uses steroids \pm IVIG as described below in the first 14 days of start of eltrombopag. Steroids may be used after day 14 if the dose is considered low dose as per protocol definition and/or tapered down (i.e., successively lower doses after day 14). This change applies to the derivation of all efficacy endpoints.

By clinical practice, a patient can have a bleeding event during first 7 days after eltrombopag start. Only bleeding events that happen from day 8 onwards after the eltrombopag start will

exclude a patient to reach an efficacy endpoint. This change applies to the derivation of secondary efficacy endpoints 3, 4 and 6.

In addition to descriptive statistics, box plots will also be provided for FACIT, FACT-Th6 and SF-36 questionnaire scores.

The end of study (EOS) has been revised to end of treatment (EOT).

“Sustained remission” was changed to “sustained response off treatment”.

Starting dose for Asian patients and Japanese patients in Japan described.

Study objective and endpoints updated in accordance with clarifications of the protocol: described above.

Section 2.1.1 The formula for the duration of exposure was clarified. Definition of the planned dose provided. Descriptions of observation periods clarified.

Section 2.4.2 (Rescue therapy) created.

Sections 2.5.1, 2.5.2, 2.5.3 was updated with descriptions of the primary endpoint calculations: using of scheduled/unscheduled visits, possibility of re-attempt steps 1-3, handling of missing platelets counts at scheduled visits.

Section 2.8.2 The description of deaths reporting was updated.

Section 2.8.4.4 (bleeding adverse events) was created.

Section 1. Timelines were updated. Section 2.1. Cutoff date is provide. Formula of the duration of exposure is updated. Clarified the description of the using cutoff date instead missing the end date.

Section 2.2.1. Provided details of the sub-group analysis.

Section 2.5.2. Updated the description of the listings. Provided clarifications of the conditions for achieving the Step 3.

Section 2.7.2. The analysis description was updated, added the event description, censoring rules.

Section 2.8.4.4. Title updated

5 Appendix

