2.4.2 Rescue therapy

Any ITP-directed medication or therapy, other than eltrombopag, given during the trial with the aim to increase platelet count for the patients who have clinically significant bleeding will be considered a rescue therapy and must be recorded on the appropriate CRF page (Form: Concomitant Medication, the category value at the form: Rescue medication). A patient who receives rescue medication or therapy between Step 2 and Step 3 will not be eligible for Step 3. A patient who receives rescue medication or therapy between Step 3 and Step 4 will not be eligible for Step 4. A patient who receives rescue medication or therapy will not be considered in having achieved sustained response off treatment for the primary endpoint, unless the patient uses steroids ± IVIG as described below in the first 14 days of start of eltrombopag.

Steroids ± IVIG use as rescue medication:

In case of clinical need such as very low platelet count (<10×10⁹/L) and/or significant bleeding, treatment with steroids ± IVIG and platelet transfusion is permitted together with eltrombopag for the first 14 days, calculated from the first dose day of eltrombopag. Any rescue therapy started before Day 14 may be used after Day 14 if the dose is considered low dose as per protocol definition and is being tapered down (i.e., successively lower doses after day 14).

Rescue medication will be taken from the SDTM cm.sas7bdat dataset where cmcat='RESCUE MED' for rescue therapy and exported as an EXCEL file. The clinical team will review the records captured in an Excel spreadsheet. Medications which were not considered as rescue therapy were flagged as 'Y' for the column 'NOT_RESCUE'. Per protocol, medications prior to Day 14 are not considered as rescue medication in the efficacy derivations and will be programmatically excluded. Medications that started prior to Day 14 and were still being tapered after Day 14 will also be programmatically excluded from efficacy derivations.

Once the database has locked the data will be rechecked again for any changes or new data that needs flagging.

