The spreadsheet will contain patient level data with patient number (USUBJID), sequence number (CMSEQ), reported drug name (CMTRT), standardized medication name (CMDECOD), category for medication (CMCAT), indication (CMINDC), dose per administration (CMDOSE), dose units (CMDOSU), dosing frequency per interval (CMDOSFRQ), start date/time of medication (CMSTDTC), end date/time of medication (CMENDTC), indication 1(CMINDC1), indication 2 (CMINDC2), reported name of drug trade name (CMTRDNAM), not rescue medication flag (NOT_RESCUE).

The spreadsheet will be imported into the programming environment (GPS) and merged with the patient data for the analysis. The EXCEL document will be stored in CREDI in the study folder ETB115J2411/Administrative Files (study level)/RAP or RAMP Meeting and in GPS in the study folder: CETB115J2411\csr_1\util.

Platelet transfusions will be taken from the ADCM and ADPR datasets. The variables category for medication (CMCAT), standardized medication name (CMDECOD), reported name of drug, medication, or therapy (CMTRT) from the ADCM will be used for the looking for platelets transfusions. The CMCAT values should be equal to 'RESCUE MED', and CMDECOD and/or CMTRT should contain the text 'PLATELET'. The variables contained reported names of procedure (PRTRT) and standardized procedure name (PRDECOD) from ADPR will be used for the looking for platelets transfusions. The PRDECOD and/or PRTRT should contain the text 'PLATELET'.

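### The SAP gives conflicting rules for scoring early rescue that continues past Day 14, and endpoints 3 and 6 still read as free of bleeding and rescue although early events are removed

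*SAP*

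**What the plan says.** Protocol 6.2.3 denies sustained remission on the primary endpoint to any patient who receives rescue, with one exemption: steroids with or without IVIG during the first 14 days, counted from the first dose. It makes no provision for a low dose or a taper beyond that window, and it names no other endpoint.

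SAP 2.4.2 repeats that rule and then adds to it. Its text says "Any rescue therapy started before Day 14 may be used after Day 14", but only "if the dose is considered low dose as per protocol definition and is being tapered down". Its programming paragraph says "Per protocol, medications prior to Day 14 are not considered as rescue medication in the efficacy derivations and will be programmatically excluded" and then "Medications that started prior to Day 14 and were still being tapered after Day 14 will also be programmatically excluded from efficacy derivations". That last sentence carries no dose condition. A clinical-team review also applies: "Medications which were not considered as rescue therapy were flagged as" Y in a NOT_RESCUE column, and "The spreadsheet will be imported into the programming environment (GPS) and merged with the patient data for the analysis".

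SAP 2.5.2 lists when a patient cannot be counted at Step 4, the primary endpoint: early rescue whose dosage was raised after day 14, new rescue after day 14, or a platelet transfusion after day 14.

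SAP section 4, on changes from the protocol, says "Steroids may be used after day 14 if the dose is considered low dose as per protocol definition and/or tapered down" and adds "This change applies to the derivation of all efficacy endpoints". It also ignores bleeding on Days 1 to 7 for secondary endpoints 3, 4 and 6.

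SAP 2.7.2 still words endpoint 3 (a count of at least 50 in the first month) and endpoint 6 (maintaining at least 30) as being without bleeding events or rescue therapy.

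**The concern.** Whether continued rescue counts against a patient is part of the primary endpoint definition, so it needs a single answer. Here the sections differ on which conditions must be met (both, either, taper only, or no dose increase) and on what is covered (any rescue in 2.4.2, steroids in section 4). The same patient can be a responder under one sentence and a non-responder under another. A reader of the CSR cannot tell which sentence produced the reported rate.

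For endpoint 3 the issue is what the label promises. A patient given rescue in week 1 who then reaches 50 can be reported as a responder without rescue, although the rise may owe something to the rescue.

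**Working it through.** **1. The rules side by side.** Take rescue steroids started before Day 14 and still in use afterwards. The column for 2.5.2 assumes that its list is exhaustive, which the SAP does not state.

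| Use after Day 14 | 2.4.2 text | 2.4.2 programming | Section 4 | 2.5.2 list | Protocol 6.2.3 |
|---|---|---|---|---|---|
| Low dose, tapering | excused | excused | excused | not disqualified | not exempt |
| Above low dose, tapering | not excused | excused | excused | not disqualified | not exempt |
| Low dose, constant | not excused | not excused | excused | not disqualified | not exempt |
| Above low dose, constant | not excused | not excused | not excused | not disqualified | not exempt |

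Rows 2 and 3 conflict between 2.4.2 and section 4 however 2.5.2 is read. Row 4 conflicts only if the 2.5.2 list is exhaustive. That makes two of four patterns for certain and three of four on that reading. Row 1 is consistent within the SAP but departs from the protocol.

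**2. The Day 14 boundary.** SAP 2.1.1 makes the first dosing day Day 1, so the protocol window is Days 1 to 14. The 2.4.2 wording removes medication before Day 14, that is Days 1 to 13. The 2.5.2 list disqualifies new rescue after day 14, that is from Day 15. Rescue started on Day 14 is therefore inside the protocol window and not disqualified by 2.5.2, but it is not removed by 2.4.2.

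**3. Whether other controls settle it.** 2.4.2 bars rescue between Steps 2 and 3 and between Steps 3 and 4. Step 2 needs two months after a count of at least 100. With the first weekly count after the start at about Day 8 and the SAP month of 365.25/12 = 30.4375 days, Step 2 comes no earlier than about 8 + 2 × 30.4375 = Day 68.9. Rescue that ends before then is not caught. How NOT_RESCUE combines with the programmed exclusions is not stated; the programming specification is a separate document and was not available.

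**4. What one patient is worth.** Inputs from SAP 3.1.2: N = 105, P0 = 0.15, P1 = 0.25, reject at 23 or more. The exact binomial tail P(X ≥ r | N, p) first reproduces the plan:
- N = 101, r = 22: alpha 0.0433, power 0.8042 (SAP: 0.043, 0.804).
- N = 105, r = 23: alpha 0.0373, power 0.7995 (SAP: 0.037, 0.800).

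Then, with N = 105 and P0 = 0.15:
- 23 responders: p = 0.0373.
- 22 responders: p = 0.0626.
- 26 responders (0.25 × 105 = 26.25): p = 0.0060. Significance is lost only at 22, that is after 26 − 22 = 4 reclassifications.
- P(X = 23 | p = 0.25) = 0.071, so landing exactly on the cut-off is uncommon at the design rate.

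**5. Endpoint 3.** Rescue is ignored for 13/30.4375 = 42.7% of the month and bleeding for 7/30.4375 = 23.0%. These are shares of the calendar window, not effects on the rate. Each responder with early rescue or early bleeding would lower the strictly scored rate by 1/105 = 0.95 percentage points.

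**The case against.** The strongest reply is that section 4 exists to record departures from the protocol, and it does so: it restates the 6.2.3 rule, states the change and gives its scope. It also says that the Day 7 bleeding rule applies to endpoints 3, 4 and 6. That stands. A reader might infer an undisclosed loosening of the primary endpoint, and the documents do not support it. What section 4 leaves open is which of the versions was run.

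Second, the programming sentence in 2.4.2 may be shorthand for the fuller text above it, applied after the clinical review. That is possible and cannot be checked without the specification. It would not remove the gap between the 2.4.2 text and section 4, or between either and 2.5.2.

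Third, the low-dose definition is not in the available protocol text, but it may be redacted, so its absence is not counted as a defect. Nor is it right to call the SAP looser in every respect: on start date, 2.4.2 is one day narrower than the protocol.

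Fourth, the endpoint 3 and 6 point is about labelling. Footnotes may sit in the table shells, which were not available. That limits its weight, but the endpoint wording in the SAP is unchanged. The words *Per protocol* in 2.4.2 have no basis for secondary endpoints, because 6.2.3 names only the primary one.

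**Conclusion.** The concern holds as an inconsistency to be reconciled. The SAP gives conflicting scoring rules for early rescue continued past Day 14: two of four patterns conflict between 2.4.2 and section 4, and a third if the 2.5.2 list is exhaustive. Each rule credits some use after Day 14 that protocol 6.2.3 does not exempt. Endpoints 3 and 6 are described more strictly than they are derived.

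The number of patients affected cannot be found from the documents and is probably small. A reader might infer that the primary result is inflated or would reverse under protocol scoring. Nothing in the documents shows that: one patient decides the test only at exactly 23 of 105, and at the design rate four would have to change status. The effect on the endpoint 3 rate is likewise unknown. The point should be fixed because the executed rule cannot be identified and the final CSR is still to be written.

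**What to change.** These changes concern scoring and reporting only; no clinical rule on rescue is proposed.

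1. Reconcile SAP 2.4.2, 2.5.2 and section 4 to the one rule executed for the primary CSR. State the low-dose threshold used, how Day 14 itself is scored, and how NOT_RESCUE interacts with the programmed exclusions.
2. In the final CSR, add a sensitivity analysis: the primary binomial test under protocol 6.2.3 scoring, with the number of patients whose status changes.
3. Relabel endpoints 3 and 6 to state the early rescue and early bleeding exclusions. For endpoint 3, report how many responders had early rescue or bleeding. Beside the main rate, show the rate with those early events counted, and state whether events after the first count of at least 50 also count.
4. Remove *Per protocol* from the 2.4.2 sentence as far as it concerns secondary endpoints.

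The cost is SAP wording and one or two extra tables from medication and adverse-event data already collected. The primary CSR is not reopened and no main analysis changes. The downside is that rates under strict scoring may be lower than those reported.

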6. To assess the ability of eltrombopag to maintain platelet count $\geq 30 \times 10^9/L$ within 12 months and every 3 months until month 24	6. Number (%) of patients who maintain a platelet count $\geq 30 \times 10^9/L$ from the first time of reaching that level to month 3, 6, 9, 12, 15, 18, 21, 24, and end of treatment without bleeding and no rescue therapy

Objective(s)	Endpoint(s)
7. To evaluate patient-Health Related outcome measures for health-related quality of life (fatigue level of the patients through FACIT) & FACT-Th6 and SF-36v2 questionnaires from baseline and every 3 months to month 24 and end of treatment	7. The analysis of HRQoL parameters; fatigue level of the patients through FACIT & FACT-Th6, SF-36v2 questionnaires. Change in scores from baseline to month 3, 6, 9, 12, 15, 18, 21, 24, and end of treatment
8. To explore the overall impact of side effects on treatment via the GP5 at baseline, month 12, and end of treatment	8. Overall change from baseline to month 12 and end of treatment will be assessed
9. To explore treatment satisfaction with TSQM-9 at baseline, month 12, and end of treatment	9. Overall change from baseline to month 12 and end of treatment will be assessed
10. To evaluate the safety and tolerability of eltrombopag	10. Number (%) and severity of patients with AEs, serious AEs (SAEs), AEs leading to discontinuation, AEs leading to dose adjustments, AEs of special interest. Change from baseline in vital signs and clinical laboratory tests

[figure not shown]
FACIT=Functional Assessment of Chronic Illness Therapy; FACT=Functional Assessment of Cancer Therapy; FACT-Th6=Functional Assessment of Cancer Therapy – Thrombocytopenia 6-item version; GP5-bothered by symptoms component of the FACT-G assessment; HRQoL=Health Related Quality of Life; SF-36=Short Form-36; [REDACTED]

TSQM-9=Treatment Satisfaction Questionnaire for Medication; [REDACTED]

3 Study design

This is a phase II, open-label, prospective, single-arm, study to assess ability of eltrombopag to induce sustained remission in adult patients with ITP who are refractory or relapsed after first line steroids. The study design is provided in [Figure 3-1](#).

Figure 3-1 CETB115J2411 study design

*Sustained remission is defined as patients who:

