12.4.1 Definition of primary endpoint

The primary endpoint is the proportion of patients with sustained remission (R) by month 12.

Sustained remission (R) is defined as:

- reach platelet count $\geq 100 \times 10^9 / \text{L}$ (CR) and then maintain platelet counts around $100 \times 10^9 / \text{L}$ for 2 months (no counts below $70 \times 10^9 / \text{L}$) **AND** then
- taper off the drug until treatment discontinuation (see [Section 9.1](#)) while,
- maintain platelet count $\geq 30 \times 10^9 / \text{L}$ in the absence of bleeding (no bleeding AEs) or use of any rescue therapy (see [Section 6.2.3](#)) until month 12.

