26-Apr-2022	After iDBL for Primary CSR at Month 12	
Incorporate changes from protocol amendment 1 dated 06-Mar-2019
 
Terminology updating
 
Further clarifications added
	
Updated cut-off date for Primary CSR
 
Updated months reported with corresponding visits
 
Change End of Study (EOS) to End of Treatment (EOT). EOS removed from the SAP
 
Change “sustained remission” to “sustained response off treatment”
 
Study design figure updated
 
Starting dose for Asian patients and Japanese patients in Japan described
 
Study objectives and endpoints updated
 
Formula for the duration of exposure was clarified
 
Definition of planned dose provided
 
Descriptions of observation periods clarified
 
Sections 2.4.2 Rescue therapy created
 
More details for the primary endpoint calculation provided
 
More details for the primary endpoint calculation provided
 
More details of the analysis provided
 
The description of deaths reporting clarified
	
2.1
 
2.1
 
Throughout SAP
 
Throughout SAP
 
1.1
 
2.1.1
 
2.4.2
 
2.5.1
 
2.5.2
 
2.5.3
 
2.8.2

Date	Time point	Reason for update	Outcome for update	Section impacted (Current)
			Section 2.8.4.4 Bleeding adverse events created	2.8.4.4
07-Sep-2022	Prior to final DBL for final CSR	Further clarification added	Time points updated The names of GPS folder added Data analysis information updated General definitions updated	1 1 2.1 2.1.1
		Analysis updated	Provided details about the subgroup analysis	2.2.1
		Further clarification added	Provided details about the data presenting Provided details for Step 3 achieving	2.5.2 2.5.2
		Further clarification added	No imputation will be used fro missing platelet values (deleted original sentence to avoid confusion)	2.5.3
		Analysis updated	Updated the description of the analysis	2.7.2
			Title updated	2.8.4.4
		Missing references	References are provided	6

FPFV: First patient first visit

TEMPLATE VERSION AND DATE: Final 2.0 25-Apr-2016, Effective 03-May-2016

Table of contents

Table of contents	5
List of abbreviations	7
1 Introduction	9
1.1 Study design.....	9
1.2 Study objectives and endpoints	12
2 Statistical methods.....	13
2.1 Data analysis general information	13
2.1.1 General definitions.....	14
2.2 Analysis sets	17
2.2.1 Subgroup of interest	18
2.3 Patient disposition, demographics and other baseline characteristics	18

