PGIS	Patient Global Impression-Severity

PRO	Patient-reported Outcomes
PT	Preferred Term
QD	Qua'que di'e / once a day
SAP	Statistical Analysis Plan
SD	Standard Deviation
SE	Standard Error
SF-36	Short Form 36
SOC	System Organ Class
SRoT	Sustained response off treatment
TBIL	Total Bilirubin
TEAE	Treatment-emergent Adverse Events
[REDACTED]	[REDACTED]
TPO-RA	Thrombopoietin Receptor Agonists
TSQM	Treatment Satisfaction Questionnaire for Medication
ULN	Upper Limit of Normal
WBC	White Blood Cells
[REDACTED]	[REDACTED]

1 Introduction

This statistical analysis plan (SAP) provides detailed statistical methodology for the analyses of data which will be used for the preparation of the ETB115J2411 (TAPER) clinical study reports (CSRs) and is based on the study protocol amendment 1, dated 06-Mar-2019. All patients (105) have been enrolled in the trial at the time of Addendum 1 and the primary CSR was final at the time of this Addendum 2.

During the course of this study, there are two planned reporting events:

[figure not shown]
- Primary analysis was done after all patients were enrolled and either discontinued early from the study or completed 12 months on study. The primary Clinical Study Report (CSR) was written at this time point. The data cutoff for primary analysis was 22-Oct-2021 and the interim database lock (iDBL) was on 29-Apr-2022.
- Second analysis will be done after all patients in the follow-up period have completed month 24. The final CSR will be written at this time point.

The shells for the in-text tables and figures as well as the post-text tables, figures and listings (TFLs) are in the TFL shells document. Programming specifications for datasets, including derivation of variables, are given in the programming data specifications (PDS) document.

All data will be analyzed by Novartis in Novartis global programming & statistical (GPS) environment, or by a designated CRO. Analysis data sets and statistical outputs will be produced using the SAS system Version 9.3 or higher. Primary CSR datasets and outputs are in GPS folder CSR1 and the final CSR datasets and outputs will be in GPS folder CSR2.

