2.5.2 Statistical hypothesis, model, and method of analysis

The number (%) of patients with sustained response off treatment by month 12 will be summarized together with 95% confidence interval (CI) using the Clopper-Pearson method.

A binomial test for one proportion, $H_0: P=0.15$ vs. $H_1: P>0.15$ will be performed to test if the proportion of sustained response off treatment patients is greater than 15% using a target alpha level of 0.05.

Listing for hematologic response, with flags for: platelets $<30 \times 10^9 / L$, bleeding events, transfusions, and rescue medications will be provided. Steps until sustained response off treatment at month 12 and during the follow-up period will be flagged as follows:

- Patients who reached platelet count $\geq 100 \times 10^9 / L$ at least once
- Patients who maintained stable platelet count for 2 months after reaching $100 \times 10^9 / L$ (no counts below $70 \times 10^9 / L$)
- Patients who were able to be tapered off the drug till treatment discontinuation, while maintain platelet count $\geq 30 \times 10^9 / L$ in the absence of bleeding (no bleeding AEs) or use of any rescue therapy
- Patients with sustained response off treatment until month 12, while maintain platelet count $\geq 30 \times 10^9 / L$ in the absence of bleeding (no bleeding AEs) or use of any rescue therapy
- Patients with sustained response off treatment from month 12 to month 24, while maintain platelet count $\geq 30 \times 10^9 / L$ in the absence of bleeding (no bleeding AEs) or use of any rescue therapy

The patients can re-attempt Steps 1 to 3.

The patient cannot be considered as having achieved SRoT (step 4) in the cases below:

1. If a patient has taken rescue med prior to day 14 and if the dosage was increased after day 14 they are not considered as Step 4 at month 12.
2. If a patient has taken new rescue med after day 14 they are not considered as Step 4 at month 12.
3. If a patient taken platelet transfusion after day 14 they are not considered as Step 4 at month 12.

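### Several responder-derivation rules differ from the protocol and are logged six months after the last month-12 visit of an open-label trial, with no protocol-rule count shown beside them

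*SAP*

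**What the plan says.** Protocol 12.4.1 fixes the endpoint: "The primary endpoint is the proportion of patients with sustained remission (R) by month 12". Protocol 12.4.2 tests it against 15% with a one-sided binomial test. SAP 2.5.2 keeps this and will "test if the proportion of sustained response off treatment patients is greater than 15% using a target alpha level of 0.05". SAP 3.1.2 sets the rule at the final sample size: reject with 23 or more responders of 105, actual alpha 0.037.

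SAP section 4 (Changes to protocol specified analyses) records that 2.5.1 to 2.5.3 were updated on "using of scheduled/unscheduled visits, possibility of re-attempt steps 1-3, handling of missing platelets counts at scheduled visits", and that 2.4.2 on rescue therapy was created. The document history puts both in the entry of 26-Apr-2022, whose time point reads "After iDBL for Primary CSR at Month 12". SAP section 1 states: "The data cutoff for primary analysis was 22-Oct-2021 and the interim database lock (iDBL) was on 29-Apr-2022". SAP 2.1 identifies the cut-off as the last patient's Week 53 visit.

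The next entry, 07-Sep-2022, includes "Provided details for Step 3 achieving" for 2.5.2 and the deletion of a sentence from 2.5.3. SAP section 1 says "the primary CSR was final at the time of this Addendum 2".

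The final CSR uses month-12 status to split outputs (SAP 2.2.1, 2.7.2 and 2.8.1).

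**The concern.** Protocol section 3 describes the study: "This is a phase II, open-label, prospective, single-arm, study to assess ability of eltrombopag to induce sustained remission in adult patients". With no blinding and no control arm, platelet counts, rescue use and dosing are known as they accrue. The protection against choosing rules to suit the data is that the rules are fixed beforehand. Here, rules that decide individual responder status are logged after every month-12 visit had taken place. The plan does not say when each was first set, does not mark any as post hoc, and asks for no count under the protocol rules.

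The primary decision is a count against a threshold, so a small number of reclassified patients could matter. The later edits raise a second question. SAP 2.4.2 and 2.8.4.4 have the clinical team's rescue and bleeding flags rechecked after lock, and 2.8.4.4 names separate storage for each report. If month-12 status is re-derived for the final CSR, a patient could be a responder in one report and not in the other, and every analysis split by that status would shift.

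**Working it through.** **Step 1. Dates.** Inputs: last Week 53 visit and cut-off 22-Oct-2021 (SAP 2.1); interim lock 29-Apr-2022 (SAP 1); log entries 26-Apr-2022 and 07-Sep-2022 (SAP document history), taken here as Addenda 1 and 2.
- Cut-off to Addendum 1: 9+30+31+31+28+31+26 = 186 days.
- Addendum 1 to the stated lock: 3 days. The entry is labelled as after a lock that section 1 dates later.
- Stated lock to Addendum 2: 1+31+30+31+31+7 = 131 days.

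Whichever lock date is right, Addendum 1 follows the last month-12 visit.

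**Step 2. Rules side by side.**

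| Rule | Protocol | SAP | Direction |
|---|---|---|---|
| (a) Missing counts | 12.4.3: missing assessments mean the patient is not counted in remission | 2.5.3: that sentence is absent; at least two counts, 14 or more days apart, are required | Can add responders |
| (b) Rescue | 6.2.3: exception confined to the first 14 days | 2.4.2 and section 4: exception extends past Day 14 for low-dose or tapered use | Can add responders |
| (c) Visits | 8.3.1 allows extra counts; 12.4.1 sets floors of 70 and 30 without limiting them to scheduled counts | 2.5.1: only scheduled counts to month 12 | Mostly adds (a low unscheduled count no longer disqualifies); can lose a patient whose CR appears only at an unscheduled visit |

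On (a), two months is 2 × 30.4375 = 60.875 days. At fortnightly visits that spans 60.875/14 ≈ 4.3 intervals, so about half of the expected counts could be missing. The log does not reproduce the sentence deleted in September 2022, so it is unknown whether it was the protocol's missing-assessment rule.

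On (b), the log dates the creation of 2.4.2 to Addendum 1, but the section 4 paragraph is undated. The condition is joined by *and* in 2.4.2 and by *and/or* in section 4; the two must be reconciled.

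**Step 3. Reproduce the plan's figures.** P(X ≥ c) = Σ from x=c to N of C(N,x) p^x (1−p)^(N−x).
- N=101, c=22: alpha 0.0433, power at 25% 0.804 (stated 0.043, 0.804).
- N=105, c=23: alpha 0.0373, power 0.7995 (stated 0.037, 0.800).

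Both reproduce.

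**Step 4. The boundary.** At N=105, 23 responders (21.9%) give p=0.0373, which rejects. Twenty-two (21.0%) give p=0.0626, which does not.

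**Step 5. Illustration of size.** Assumption: the true rate under the protocol rules is 15%, and the later rules change the count by a net k patients. The documents do not give k. The chance of rejecting is P(X ≥ 23−k | 105, 0.15):

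| Net k | −1 | 0 | 1 | 2 | 3 |
|---|---|---|---|---|---|
| P(reject) | 0.021 | 0.037 | 0.063 | 0.100 | 0.153 |

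Alternatively, if each protocol failure becomes a responder with probability f, the rate is 0.15 + 0.85f. For f = 1%, 2%, 3% the rates are 0.1585, 0.1670 and 0.1755, and the chances of rejecting are 0.063, 0.100 and 0.148.

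**The case against.** The strongest reply is that nothing essential changed. The definition, the Full Analysis Set, the 15% null, the exact test and the 0.05 target all stand in the protocol, and protocol section 12 leaves further detail to the SAP. The log describes the edits as details and clarifications, and section 4 discloses them. This stands, and it rules out several stronger readings that a reader might infer:

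- *The endpoint was not pre-specified.* It was. Only some derivation rules lack a demonstrated earlier date.
- *The changes can only add responders.* Rule (c) can also remove one. Re-attempts are partly foreseen, since protocol Table 6-1 covers patients who regain CR or are re-treated, and 12.4.1 does not limit the definition to a first attempt.
- *There are three versions of the endpoint.* The Step 3 conditions now in SAP 2.5.2 match the taper conditions in protocol 12.4.1, and the effect of the sentence deleted in September 2022 is unknown. Addendum 2 postdates the primary CSR and cannot have altered the test reported there.
- *The formal test must be re-based on the protocol text.* The earlier SAP text is not available. It may have held some of these rules, including the rescue extension.
- *Someone saw responder counts and then chose the rules.* No passage shows this.

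The reply does not remove the three departures in substance, their log dates, or the absence of a comparison that would show whether they matter. The illustration in Step 5 is hypothetical: it assumes a net shift and holds the 15% null to the protocol derivation, although protocol 4.1 itself calls that figure postulated.

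**Conclusion.** The point holds as a matter of derivation and timing. Three responder rules differ from the protocol. The log places the edits to 2.5.1–2.5.3 and the creation of 2.4.2 186 days after the last Week 53 visit of an open-label trial, with the reservation above on dating the rescue extension. Further edits came after the primary CSR was final.

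The net direction is mainly permissive. The actual effect is unknown, because the number reclassified is not in the documents. If the count is well clear of 23 under both sets of rules, the conclusion is unaffected. If it is close, one patient can decide it, and a net gain of one to three responders would put the chance of a false rejection at 0.063 to 0.153 instead of 0.037. Those figures rest on the assumed net gains and on a true protocol-rule rate of 15%. The stated error rate is assured only if the rules were fixed without sight of outcomes, which the plan does not establish.

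**What to change.** In SAP 2.5.2, 2.5.4 and section 4:

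1. Add a sensitivity analysis of the month-12 responder count under the protocol rules: all counts including unscheduled ones, missing assessments as non-response, and the rescue exception limited to the first 14 days. Give n, %, the 95% Clopper-Pearson interval and whether the count reaches 23 of 105, beside the SAP derivation. List each patient whose status differs, with the rule responsible. Protocol 12.4.3 does not say how many missing counts disqualify, so state the reading used; counting any missing scheduled assessment as failure is the strictest.
2. For each rule, state when it was first set relative to the 22-Oct-2021 cut-off and the interim lock. Label any rule first set after the cut-off as post hoc. If an earlier SAP already held a rule, citing it closes that part.
3. Use month-12 status as reported in the primary CSR for all final-CSR outputs, and show any reclassification separately.
4. Reconcile the time-point label on the 26-Apr-2022 entry with the 29-Apr-2022 lock date, and the two wordings of the post-Day-14 rescue condition.

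The cost is SAP wording, one extra derivation and one listing, all from data already held. The downside is that a second, possibly lower, rate appears beside the headline rate.
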